#### Censoring

Time to event endpoints are defined from the date of first dose of IP.

If the subject did not have an event, the time to event will be censored at the last contact date, as defined in Section 6.5.

#### Sensitivity Analyses

An on-treatment approach will be performed for the key secondary endpoint of time to first respiratory hospitalization.

#### Additional Analysis

The number of subjects with 0, 1, 2, 3, >3 respiratory-related hospitalizations will be presented by treatment group.

Since it is expected that a relatively high number of subjects will have more than one hospitalization, the rate of hospitalizations will be compared between each of the dose groups and placebo using a negative binomial model (generalized linear model) as explained in Keene et al. (2007).

#### 9.3.3.1. Other Adjudicated Events (Secondary) Endpoints

A time to (first) event analysis will be conducted for each of the following secondary endpoints:

- Mortality: all-cause and respiratory-related
- Hospitalization: all-cause
- Hospitalization for non-elective Lung transplant
- Acute IPF exacerbation
- All-cause mortality or hospitalization for non-elective lung transplant
- All-cause mortality, or hospitalization for non-elective lung transplant, or hospitalization for qualifying for lung transplant
- All-cause mortality, hospitalization for ≥10% absolute decline in %FVC, or respiratoryrelated hospitalizations
- All-cause mortality or respiratory-related hospitalizations

Results will be based on the results coming from adjudication. Time to first event will be presented for each type of adjudicated event, similarly as time to first respiratory-related hospitalizations, using Kaplan-Meier tables, graphs and Cox PH models based.

In addition, for all-cause hospitalization and all-cause mortality a frequency table will be provided for the primary cause of death/hospitalization as defined by the CEAC.

Respiratory related events analyses will also be provided by stratification factor (standard of care).

In addition to the analysis of all-cause mortality based on adjudication, a time to all-cause mortality analysis will also be performed on all-cause mortality as reported by the investigator.

Analyses to assess the impact of COVID-19 cases (infection and suspected) on mortality and disease progression will be provided.

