4.3.2.2. Other Secondary Endpoints

- Rate of decline of FVC (in mL) until the end of the study
- Disease progression defined as the composite endpoint of first occurrence of $\geq 10\%$ absolute decline in %FVC or all-cause mortality until the end of the study
- Change from baseline in the SGRQ total score until the end of the study
- Time to first all-cause non-elective hospitalization until the end of the study
- Time to respiratory-related mortality until the end of the study
- Time to lung transplant until the end of the study
- Time to first acute IPF exacerbation until the end of the study
- Time to all-cause mortality or lung transplant until the end of the study
- Time to all-cause mortality, or lung transplant, or qualifying for lung transplant until the end of the study
- Time to all-cause mortality, $\geq 10\%$ absolute decline in %FVC, or respiratory-related hospitalizations until the end of the study
- Time to all-cause mortality or respiratory-related hospitalizations until the end of the study
- FVC analyses at 52 weeks and until the end of the study:
 - absolute and relative change from baseline of FVC and %FVC
 - absolute categorical change of %FVC until the end of the study: decrease by >5 , increase by >5 , and change within ≤ 5
 - absolute categorical change of %FVC until the end of the study: decrease by >10 , increase by >10 , and change within ≤ 10
- Safety and tolerability over time until the end of the study
- Changes from baseline in cough-related quality of life, assessed by the LCQ total score and domains over time, and the VAS Cough and Urge to Cough, at 52 weeks and until the end of the study

- Changes from baseline in quality of life, assessed by the EQ-5D, K-BILD total score and domains over time, at 52 weeks and until the end of the study
- Plasma concentration of GLPG1690, pirfenidone, and nintedanib (as appropriate) at 52 weeks and until the end of the study
- Change from baseline in functional exercise capacity, assessed by the 6MWT distance, at 52 weeks and until the end of the study
- Change from baseline in DLCO (corrected for hemoglobin [Hb]) at 52 weeks and until the end of the study

4.3.3. [REDACTED]

- [REDACTED]
- [REDACTED]
- [REDACTED]
- [REDACTED]
- [REDACTED]
- [REDACTED]
- [REDACTED]

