6.5.2. Clinical Endpoints

A time to (first) event analysis will be conducted for each of the following secondary endpoints:

- Mortality: all-cause and respiratory-related
- Hospitalization: all-cause and respiratory-related
- Lung transplant
- Acute IPF exacerbation
- All-cause mortality or lung transplant
- All-cause mortality, or lung transplant, or qualifying for lung transplant
- All-cause mortality, $\geq 10\%$ absolute decline in %FVC, or respiratory-related hospitalizations
- All-cause mortality or respiratory-related hospitalizations

These endpoints will be adjudicated by the CEAC (for details, refer to Section 8.2).

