#### 2.2.3. Other Secondary Endpoints

- Rate of decline of FVC (in mL) until the end of the study
- Disease progression defined as the composite endpoint of first occurrence of ≥10% absolute decline in %FVC or all-cause mortality until the end of the study
- Change from baseline in the SGRQ total score until the end of the study
- Time to first all-cause non-elective hospitalization until the end of the study
- Time to respiratory-related mortality until the end of the study
- Time to lung transplant until the end of the study
- Time to first acute IPF exacerbation until the end of the study

- Time to all-cause mortality or lung transplant until the end of the study
- Time to all-cause mortality, or lung transplant, or qualifying for lung transplant until the end of the study
- Time to all-cause mortality, ≥10% absolute decline in %FVC, or respiratory-related hospitalizations until the end of the study
- Time to all-cause mortality or respiratory-related hospitalizations until the end of the study
- FVC analyses at 52 weeks and until the end of the study:
  - absolute and relative change from baseline of FVC and %FVC
  - absolute categorical change of %FVC until the end of the study: decrease by >5, increase by >5, and change within ≤5
  - absolute categorical change of %FVC until the end of the study: decrease by >10, increase by >10, and change within ≤10
- Safety and tolerability over time until the end of the study
- Changes from baseline in cough-related quality of life, assessed by the LCQ total score and domains over time, and the VAS Cough and Urge to Cough, at 52 weeks and until the end of the study
- Changes from baseline in quality of life, assessed by the EQ-5D, K-BILD total score and domains over time, at 52 weeks and until the end of the study
- Plasma concentration of GLPG1690, pirfenidone, and nintedanib (as appropriate) at 52 weeks and until the end of the study
- Change from baseline in functional exercise capacity, assessed by the 6MWT distance, at 52 weeks and until the end of the study
- Change from baseline in DLCO (corrected for hemoglobin [Hb]) at 52 weeks and until the end of the study

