#### 2.2.5. Adjudication

These endpoints will be adjudicated by the clinical endpoint adjudication committee (CEAC):

- Mortality: all-cause and respiratory-related (2 separate endpoints)
- Hospitalization: all-cause and respiratory-related (2 separate endpoints)
- Hospitalization for non-elective lung transplant
- Acute IPF exacerbation
- All-cause mortality or hospitalization for non-elective lung transplant (composite endpoint)

- All-cause mortality, or hospitalization for non-elective lung transplant, or hospitalization for qualifying for lung transplant (composite endpoint)
- All-cause mortality, hospitalization for  $\geq 10\%$  absolute decline in %FVC, or respiratory-related hospitalizations (composite endpoint)
- All-cause mortality or respiratory-related hospitalizations (composite endpoint)

Adjudication endpoints will be used in the analyses and not the corresponding investigatorreported events. Consistency with the investigator-reported information will be investigated, however.

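### SAP 2.2.5 and 9.3.3.1 make four secondary time-to-event endpoints depend on hospital admission, contrary to the protocol and SAP 2.2.3, and SAP 9.1 does not record the change

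*SAP*

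**What the plan says.** The protocol defines these endpoints by the event. Protocol 4.3.2.2 has, for example, "Time to all-cause mortality, or lung transplant, or qualifying for lung transplant until the end of the study", and the list sent for adjudication in Protocol 6.5.2 has "All-cause mortality, or lung transplant, or qualifying for lung transplant". SAP 2.2.3 repeats the protocol's list, including "Time to all-cause mortality, ≥10% absolute decline in %FVC, or respiratory-related hospitalizations until the end of the study". No admission is required for the transplant, qualifying or %FVC components.

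Two later SAP sections differ. SAP 2.2.5 has "All-cause mortality, or hospitalization for non-elective lung transplant, or hospitalization for qualifying for lung transplant (composite endpoint", and SAP 9.3.3.1 has "All-cause mortality, hospitalization for ≥10% absolute decline in %FVC, or respiratoryrelated hospitalizations". Lung transplant alone, and death or transplant, are restricted in the same way, to an admission for a transplant that is not elective.

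Both sections make the adjudicated version the one that is analysed. SAP 2.2.5 says "Adjudication endpoints will be used in the analyses and not the corresponding" investigator-reported events, and SAP 9.3.3.1 says "Results will be based on the results coming from adjudication".

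Protocol section 7 requires departures from its planned analyses to be documented in the SAP. SAP 9.1 is the section for that purpose. It lists omitted analyses and added COVID-19 outputs, and no change to an endpoint definition.

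**The concern.** A fall of at least 10 points in %FVC is found by spirometry at a study visit. It is not in itself a reason for admission. Under SAP 9.3.3.1 as written, a subject with such a fall who survives without a qualifying admission is censored as event-free in the fourth endpoint. A subject who declines first and later dies or is admitted counts, but at the later date. In the transplant endpoints, a transplant classed as elective (a term that neither document defines) and qualification for transplant without admission do not count.

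The fourth endpoint may also become redundant. If the adjudication committee classes every admission for FVC decline as respiratory-related, it is the same as death or respiratory-related hospitalization, which is listed separately. That is an inference, because the committee's charter is not in the documents.

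The SAP therefore holds two definitions of the same endpoints and does not say which governs. According to SAP 2.7, part of the study team was unblinded after the decision to terminate, so the choice should be fixed in writing. The documents do not show when the admission wording entered.

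**Working it through.** **Step 1. Compare the definitions.**

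| Endpoint | Protocol 4.3.2.2, 6.5.2; SAP 2.2.3 | SAP 2.2.5, 9.3.3.1 |
|---|---|---|
| (a) | any lung transplant | admission for a transplant that is not elective |
| (b) | death, or any transplant | death, or admission as in (a) |
| (c) | death, any transplant, or qualifying for one | death, admission as in (a), or admission for qualifying |
| (d) | death, ≥10-point %FVC fall, or respiratory admission | death, admission for such a fall, or respiratory admission |

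All four differ. Death stays unconditional in (b) to (d); the other named components become conditional on admission, except respiratory admission, which already was one. SAP 9.3.2.3 counts the same %FVC fall without admission for the first key secondary endpoint, so the SAP treats one component in two ways.

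**Step 2. Look for a record of the change.** In SAP 9.1, the entry for 9.3.3 drops only the on-treatment analysis and the negative binomial model. There is no entry for 2.2.5, 9.3.3.1 or 9.3.4. The SAP version history does not mention it. None of the four changes is recorded.

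**Step 3. See whether another section restores the protocol versions.** SAP 9.3.4 describes Kaplan-Meier and Cox analyses for other time-to-event endpoints but names none. Its censoring rule refers to Section 6.4, which defines baseline; the same rule in 9.3.3 refers to 6.5, which defines last contact. SAP 9.3.2.4 analyses FVC decline or death as time to event, but that composite has no respiratory admission component.

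**Step 4. Size of the effect on (d).** The plan gives no figure to reproduce. Inputs:
- N = 500 for one dose-placebo comparison (250 per arm, Protocol 7.1).
- h = fraction with death or respiratory admission, assumed 10-20%.
- d = further fraction with decline only and no admission, assumed 5-20%.

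SAP events = N × h. Protocol events = N × (h + d). With 1:1 allocation, SE(log HR) ≈ 2/√events, so the SE ratio is √((h + d)/h).

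| h | d | SAP events | Protocol events | Lost | SE, SAP vs protocol | Ratio |
|---|---|---|---|---|---|---|
| 10% | 5% | 50 | 75 | 33% | 0.283 vs 0.231 | 1.22 |
| 10% | 10% | 50 | 100 | 50% | 0.283 vs 0.200 | 1.41 |
| 10% | 20% | 50 | 150 | 67% | 0.283 vs 0.163 | 1.73 |
| 20% | 5% | 100 | 125 | 20% | 0.200 vs 0.179 | 1.12 |
| 20% | 10% | 100 | 150 | 33% | 0.200 vs 0.163 | 1.22 |
| 20% | 20% | 100 | 200 | 50% | 0.200 vs 0.141 | 1.41 |

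The loss for (a) to (c) cannot be sized from the documents. For transplant itself it is probably small, since surgery entails admission.

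**Step 5. A related mismatch.** Protocol 4.3.2.2 and SAP 2.2.3 limit the all-cause hospitalization endpoint to non-elective admissions. Protocol 6.5.2 has only "Hospitalization: all-cause and respiratory-related", and SAP 2.2.5 and 9.3.3.1 also drop the limit. This one begins inside the protocol.

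**The case against.** The best defence is that nothing has been replaced. SAP 2.2.3 still carries the protocol definitions, SAP 2.2.5 is about adjudication, and its rule sets committee findings against investigator reports, not against central spirometry. Protocol 8.2 leaves adjudication details to the charter, so the admission wording may only describe what triggers a review. SAP 9.3.4 could be where the event-based versions are analysed. Against this, SAP 9.3.3.1 is the analysis section, and it lists the admission-based versions as the endpoints to be analysed. Protocol 6.5.2 sends the event-based versions to the same committee, so adjudication does not need the condition. An unseen charter cannot settle a conflict within the SAP, and 9.3.4 names no endpoint.

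A second defence is that the analyses may have been dropped. The SAP marks dropped analyses in italics, and the available text may not show them. But SAP 9.1 does not list 9.3.3.1 as omitted, and that section contains a COVID-19 analysis of the kind added in version 2.0.

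Three points stand. The consequence is limited: the program was terminated, only an abbreviated report is planned, and the components of (d) are largely analysed elsewhere. The event rates in Step 4 are assumptions and show scale only. The admission wording is printed openly in the SAP; what is missing is any statement that it departs from the protocol, and why.

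**Conclusion.** The concern holds. Four of four endpoints are defined differently in SAP 2.2.5 and 9.3.3.1 than in the protocol and SAP 2.2.3, and the change is not recorded. If SAP 9.3.3.1 is followed, the result for (d) changes, because subjects with decline only stop being events. On the assumed rates, 25 to 100 of 75 to 200 protocol-defined events are lost per comparison (20-67%), and the standard error is 1.12 to 1.73 times larger. Confidence is high for the mismatch; the size depends wholly on the assumed rates. These endpoints are outside the testing hierarchy, so the harm is confined to secondary results, and the point should be fixed without being critical to the trial's main conclusion.

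**What to change.** In SAP 2.2.5 and 9.3.3.1, restore the protocol definitions of the four endpoints. Take the %FVC component from centrally read spirometry, and count any lung transplant and any recorded date of qualifying for transplant. Keep committee adjudication as in Protocol 6.5.2. If the admission-based versions are wanted, keep them as additional analyses and list them in SAP 9.1. State in SAP 9.3.4 which endpoints it covers, and correct its censoring reference. Use one definition of all-cause hospitalization in Protocol 4.3.2.2 and 6.5.2 and in SAP 2.2.3, 2.2.5 and 9.3.3.1.

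The cost is SAP wording and programming. Spirometry is already centrally read, and transplant timing is already needed to exclude later efficacy data (SAP 3.3). The sponsor must confirm that a qualifying date is recorded outside hospital; the visible schedule of activities shows none. If there is none, SAP 9.1 should give that as the reason for changing endpoint (c).

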# 9.3.4. Other Time-to-Event Endpoints

The number (%) of subjects with an event during the study will be summarized as well as the number of events per 100 patients-years of follow-up. In addition, time to first event will be graphically displayed and tabulated (at each planned time point as described in Section 6.3, Week 2, Week 4, etc, and last available time point) using Kaplan-Meier estimates.

A Cox proportional hazards model with terms for age, sex, height, and stratum will be used to estimate the hazard ratios (and 95% CI) for each dose compared to placebo.

# Censoring

Time to event endpoints are defined from the date of first dose of IP.

If the subject did not have an event, the time to event will be censored at the last contact date, as defined in Section 6.4.

# 9.3.5. Third Key Secondary Endpoint: SGRQ Scores

This questionnaire will be completed electronically, using a tablet device at the clinical study center. The SGRQ is a 50 item questionnaire split into three domains:

- symptoms (assessing the frequency and severity of respiratory symptoms),
- activity (assessing the effects of breathlessness on mobility and physical activity),
- impact (assessing the psychosocial impact of the disease).

Scores are weighted such that every domain score and the total score range from 0 to 100, with higher scores indicating a poorer health related quality of life.

Note that before completing the questionnaire the subject will have to answer a question on his/her present health. This info will be tabulated.

Gen	eral		
Q #	Question	Answer	Weight
	Check how you describe your current health	Very good	NA
		Good	NA
		Fair	NA
		Poor	NA
		Very poor	NA
Par Des	t 1 cribe how often your respiratory problems have affected	you over the past 3 months.	
Q #	Question	Answer	Weight
1	Over the past 3 months, I have coughed:	Almost every day	80.6
		Several days a week	63.2
		A few days a month	29.3
		Only with respiratory infections	28.1
		Not at all	0.0
2	Over the past 3 months, I have brought up phlegm	Almost every day	76.8
	(sputum):	Several days a week	60.0
		A few days a month	34.0
		Only with respiratory infections	30.2
		Not at all	0.0
3	Over the past 3 months, I have had shortness of breath:	Almost every day	87.2
		Several days a week	71.4
		A few days a month	43.7
		Only with respiratory infections	35.7
		Not at all	0.0
4	Over the past 3 months, I have had wheezing attacks:	Almost every day	86.2
		Several days a week	71.0
		A few days a month	45.6
		Only with respiratory infections	36.4
		Not at all	0.0
5	How many times during the past 3 months have you	More than 3 times	86.7
	suffered from severe or very unpleasant respiratory	3 times	73.5
		2 times	60.3
		1 time	44.2
		None of the time	0.0
6	How long did the worst respiratory attack last?	A week or more	89.7
		3 or more days	73.5
		1 or 2 days	58.8
		Less than a day	41.9

# Table 5SGRQ Questions/Items and Their Weights (from 0 to 100)

7	Over the past 3 months, in a typical week, how many	No good days	93.3
	good days (with few respiratory problems) have you had?	1 or 2 good days	76.6
		3 or 4 good days	61.5
		Nearly every day was good	15.4
		Every day was good	0.0
8	If you have a wheeze, is it worse when you get up in the	No	0.0
	morning?	Yes	62.0
Part	t 2 – Section 1		
Q #	Question	Answer	Weight
9	How would you describe your respiratory condition?	The most important problem I have	83.2
		Causes me quite a lot of problems	82.5
		Causes me a few problems	34.6
		Causes me no problems	0.0
10	If you ever held a job:	My respiratory problems made me stop working altogether	88.9
		My respiratory problems interfere with my job or made me change my job	77.6
		My respiratory problems do not affect my job	0.0
Part Que	t 2 – Section 2 stions about what activities usually make you feel short of	breath these days.	
I#	Question	Answer	Weight
11	Sitting or lying still.	False	0.0
		True	90.6
12	Washing or dressing yourself.	False	0.0
		True	82.8
13	Walking around at home.	False	0.0
		True	80.2
14	Walking outside on level ground.	False	0.0
		True	81.4
15	Walking up a flight of stairs.	False	0.0
		True	76.1
16	Walking up hills.	False	0.0
		True	75.1
17	Playing sports or other physical activities.	False	0.0

Part	t 2 – Section 3		
Que	stions about your cough and shortness of breath these da	ys.	
I#	Question	Answer	Weight
18	Coughing hurts.	False	0.0
		True	81.1
19	Coughing makes me tired.	False	0.0
		True	79.1
20	I am short of breath when I talk.	False	0.0
		True	84.5
21	I am short of breath when I bend over.	False	0.0
		True	76.8
22	My coughing or breathing disturbs my sleep.	False	0.0
		True	87.9
23	I get exhausted easily.	False	0.0
		True	84.0
Part	t 2 – Section 4		·
Que	stions about other effects that your respiratory problems	may have on you these days.	
I#	Question	Answer	Weight
24	My cough or breathing is embarrassing in public.	False	0.0
		True	74.1
25	My respiratory problems are a nuisance to my family, friends or neighbors.	False	0.0
		True	79.1
26	I get afraid or panic when I cannot catch my breath.	False	0.0
		True	87.7
27	I feel that I am not in control of my respiratory problems.	False	0.0
		True	90.1
28	I do not expect my respiratory problems to get any better.	False	0.0
		True	82.3
29	I have become frail or an invalid because of my	False	0.0
	respiratory problems.	True	89.9
30	Exercise is not safe for me.	False	0.0
		True	75.7
31	Everything seems too much of an effort.	False	0.0
		True	84.5
Part	t 2 – Section 5		
Que	stions about your respiratory treatment.		
I#	Question	Answer	Weight
32	My treatment does not help me very much.	False	0.0
		True	88.2
33	I get embarrassed using my medication in public.	False	0.0
		True	53.9

34	I have unpleasant side effects from my medication.	False	0.0
		True	81.1
35	My treatment interferes with my life a lot.	False	0.0
		True	70.3
Part	2 – Section 6		
Que	stions about how your activities might be affected by your	respiratory problems.	
I#	Question	Answer	Weight
36	I take a long time to get washed or dressed.	False	0.0
		True	74.2
37	I cannot take a bath or shower, or I take a long time to do	False	0.0
	it.	True	81.0
38	I walk slower than other people my age, or I stop to rest.	False	0.0
		True	71.7
39	Jobs such as household chores take a long time, or I have	False	0.0
	to stop to rest.	True	70.6
40	If I walk up one flight of stairs, I have to go slowly or	False	0.0
	stop.	True	71.6
41	If I hurry or walk fast, I have to stop or slow down.	False	0.0
		True	72.3
42	My breathing makes it difficult to do things such as walk	False	0.0
	up hills, carry things up stairs, light gardening such as weeding, dance, bowl or play golf.	True	74.5
43	My breathing makes it difficult to do things such as carry	False	0.0
	heavy loads, dig in the garden or shovel snow, jog or walk briskly (5 miles per hour), play tennis or swim.	True	71.4
44	My breathing makes it difficult to do things such as very	False	0.0
	heavy manual work, ride a bike, run, swim fast, or play competitive sports	True	63.5
Part	t 2 – Section 7		
Que	stions about how your respiratory problems usually affect	t your daily life.	
I#	Question	Answer	Weight
45	I cannot play sports or do other physical activities.	False	0.0
		True	64.8
46	I cannot go out for entertainment or recreation.	False	0.0
		True	79.8
47	I cannot go out of the house to do the shopping.	False	0.0
		True	81.0
48	I cannot do household chores.	False	0.0
		True	79.1
49	I cannot move far from my bed or chair.	False	0.0
		True	94.0

50	Tick the statement which you think best describes how your respiratory problems affects you:	It does not stop me from doing anything I would like to do	0.0
		It stops me from doing one or two things I would like to do	42.0
		It stops me from doing most of the things I would like to do	84.2
		It stops me from doing everything I would like to do	96.7

Domain scores and total score:

- Symptoms score: questions 1-8.
- Activity score: questions 11 to 17 and 36 to 44.
- Impacts score: questions 9-10, 18 to 35 and 45 to 50.
   Total score: all questions.

Each domain score is calculated separately in three steps

- The weights for all items with positive responses are summed.
- The maximum weights for missed items are deducted from the maximum possible weight for each component. The maximum weights for all missed items are deducted from the maximum possible weight for the total score.

Score =  $100 \text{ x} \frac{\text{summed weights from positive items in that component}}{\text{sum of maximum weights for all non-missing items in that component}}$ 

The total score is calculated in a similar way:

Score =  $100 \text{ x} \frac{\text{summed weights from positive items in the questionnaire}}{\text{sum of maximum weights for all non-missing items in the questionnaire}}$ 

Sum of maximum possible weights for each score:

- Symptoms: 662.5
- Activity: 1209.1
- Impacts: 2117.8
- Total: 3989.4

Note that the questionnaire requests a single response to questions 1-7, 9-10 and 50. If multiple responses are given to one of these questions then the weights for the positive responses for that question will be averaged.

In case of missing items, the following rules will be applied:

- The symptoms score will only be calculated when no more than 2 items are missing.
- The activity score will only be calculated when no more than 4 items are missing.
- The impacts score will only be calculated when no more than 6 items are missing.
- The total score will only be calculated when the 3 domain scores could be calculated.

Note that no imputation of individual missing items will be done, only the missing domain/total scores will be imputed.

Values and changes from baseline in SGRQ total score, as well as symptom, activity, and impact scores will be summarized per time point and treatment group by descriptive statistics.

A mixed-effects model with treatment, time (as a categorical factor defined by the analysis windows in Section 6.3), treatment\*time, and baseline total score as factors in the model will be applied to the SGRQ total score change from baseline. LS means (with 95% CI) will be estimated from the model at each time point for each treatment group as well as the differences from placebo in LS means (and 95% CIs). This model will be used to calculate the p-values for the SGRQ total score (key secondary endpoint) to use in the multiplicity adjustment.

A patient is an SGRQ responder if his absolute change from baseline in SGRQ total score is  $\leq$  -4 points. The number (%) of SGRQ responders at each analysis time point up to the end of the study will be presented and a logistic regression will be used to analyze the data similarly as described above for FVC responders.

In addition, a cumulative incidence table and graph will be presented for absolute change from baseline in total SGRQ score per time point and worst-case up to the end of the study for the categories  $\leq$ -4,  $\leq$ -3,  $\leq$ -2,...,  $\leq$ 0, ...,  $\leq$ 2,  $\leq$ 3,  $\leq$ 4, by treatment group.

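### SAP 9.3.5 has no rule for SGRQ item 6 (length of worst attack) when the subject reports no attacks; if item 6 is left blank, the missed-item rule slightly inflates the score

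*SAP*

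**What the plan says.** SAP 9.3.5 defines the SGRQ scores from the item weights in Table 5. Item 5 asks how often the subject had attacks over three months, and its lowest answer, "None of the time", has weight 0. Item 6 asks "How long did the worst respiratory attack last" and offers a week or more (89.7), three or more days (73.5), one or two days (58.8) and less than a day (41.9). No zero answer is listed.

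For blanks, 9.3.5 states: "The maximum weights for missed items are deducted from the maximum possible weight for each component". The total uses the same rule, with denominator "sum of maximum weights for all non-missing items in the questionnaire". It adds "Note that no imputation of individual missing items will be done". On missing items it states "The symptoms score will only be calculated when no more than 2 items are missing" and "The total score will only be calculated when the 3 domain scores could be calculated". Nothing in 9.3.5 links item 6 to the answer on item 5.

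The total score feeds a mixed model whose p-values enter the multiplicity scheme, and a responder analysis: "A patient is an SGRQ responder if his absolute change from baseline in SGRQ total score is" -4 points or lower. SAP 9.1 drops only the per-protocol and random coefficient analyses of SGRQ from the abbreviated CSR, so both remain.

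**The concern.** The deduction suits an item whose answer is unknown. After a zero on item 5, a blank item 6 will usually mean that there was no attack to time. Deducting its weight then shrinks the denominator as if the information had been lost, and since a higher score is worse, the subject's score goes up.

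This distortion depends on the outcome. It appears when a subject is free of attacks, so an improvement from attacks to none, and a worsening from none to attacks, both look smaller than they were. It reaches the key secondary model, the responder analysis and the Symptoms summaries. The blank also uses one of the two missing symptom items allowed, and the total cannot be calculated without the Symptoms score.

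**Working it through.** **The plan's own figures.** Maximum weights in Table 5, Symptoms items 1 to 8: 80.6 + 76.8 + 87.2 + 86.2 + 86.7 + 89.7 + 93.3 + 62.0 = 662.5, as stated, with item 6 included at 89.7. Impacts sum to 2117.8, as stated. The legible Activity weights sum to 1137.0. The positive weight of item 17 is not legible, and the stated 1209.1 implies 72.1 for it. Total: 662.5 + 1209.1 + 2117.8 = 3989.4, as stated.

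**Item 6 blank.** Score = 100 × summed weights / maximum weights of non-missing items.

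- Total denominator: 3989.4 − 89.7 = 3899.7; ratio 3989.4 / 3899.7 = 1.0230.
- Symptoms denominator: 662.5 − 89.7 = 572.8; ratio 662.5 / 572.8 = 1.157.

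| Total with item 6 = 0 | Total with item 6 deducted | Excess |
|---|---|---|
| 30 | 30.69 | 0.69 |
| 40 | 40.92 | 0.92 |
| 50 | 51.15 | 1.15 |
| 60 | 61.38 | 1.38 |

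A Symptoms score of 40 becomes 46.26.

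**Attacks at baseline, none at Week 52, all other answers unchanged.** Baseline totals are assumed. With baseline total B and attack-item weights w5 and w6, the Week 52 numerator is 39.894 × B − w5 − w6. Divide by 39.894 if item 6 counts as 0, or by 38.997 if it is deducted.

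| B | Attacks at baseline (w5 + w6) | Change, item 6 = 0 | Change, item 6 deducted | Lost |
|---|---|---|---|---|
| 40 | One, 1 or 2 days (44.2 + 58.8) | −2.58 | −1.72 | 0.86 (33%) |
| 45 | One, under a day (44.2 + 41.9) | −2.16 | −1.17 | 0.99 (46%) |
| 45 | Three, worst a week or more (73.5 + 89.7) | −4.09 | −3.15 | 0.94 (23%) |

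Third row in full: 39.894 × 45 = 1795.23; less 163.2 is 1632.03; divided by 39.894 gives 40.91, and by 38.997 gives 41.85. This subject is a responder in the first case and not in the second. Over baseline totals of 30 to 60 and four attack patterns, the loss is 0.59 to 1.33 points, or 13% to 62% of the attack-related change.

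**Effect on the arm difference.** Approximately (difference in attack-free share) × (excess per attack-free subject). With excesses of 0.69 to 1.15 (totals of 30 to 50):

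- 5 percentage points: 0.03 to 0.06
- 10 percentage points: 0.07 to 0.12
- 20 percentage points: 0.14 to 0.23

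Neither the attack-free share nor SGRQ levels are in the documents, so the 5 to 20 points and the totals are assumptions.

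**The case against.** The strongest reply is that 9.3.5 is silent rather than wrong. It never calls an inapplicable item 6 missed, and SAP section 1 places technical derivation details in a separate document that might hold the rule. Neither document says whether the tablet skips item 6, forces an answer or stores a zero. This stands as a limit: the inflation follows only if item 6 is blank and the general rule is applied to it. It does not cure 9.3.5, which defines an endpoint carrying a p-value and whose wording, applied literally, gives the higher score.

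A reader might infer that the score is too high whatever the tablet does. A forced answer would add at least 100 × 41.9 / 3989.4 = 1.05 points, but forcing is not documented, and a device that stores a zero would cause no error.

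A reader might also infer that item 5 at zero proves there was no attack, so that any item 6 answer should be overwritten. Item 5 is limited to attacks that were severe or very unpleasant; item 6 is not. A subject with only milder attacks can answer both truthfully, so overwriting could erase real data.

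Item 8 (wheeze worse in the morning) might seem to share the fault. It does not: it has a No answer weighted 0, which a subject without wheeze can choose. That attack-free, wheeze-free subjects routinely use up both permitted missing items is therefore not supported.

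Nor does the rule always shrink change. For a subject attack-free at both visits, change is multiplied by 1.023, so −3.92 becomes −4.01.

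Finally, SGRQ is last in each dose's testing sequence (SAP 9.3.1), and the SAP reports no treatment effect and no planned marketing application. The practical stakes are low, but the analysis is still to be reported.

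One caution: item 17's weight is illegible in the text, so a lost zero row for item 6 cannot be fully excluded. Check item 6 against Table 5; the sums of maximum weights would not reveal a missing zero.

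**Conclusion.** The point holds as a gap in 9.3.5 that, read literally for a blank item 6, gives a biased score. Conditional on the blank, the total of an attack-free subject is 2.3% too high and Symptoms 15.7% too high, relative to counting the item as 0. Changes to or from no attacks are understated; fewer or shorter attacks that do not reach none are scored normally.

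The bias can move individual subjects across the responder threshold and is most visible in the Symptoms domain. On the arm difference it is small under the assumptions above. The documents do not support saying that it would materially weaken or reverse the key secondary result. It should be corrected because the correction is cheap and the score feeds a tested endpoint.

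**What to change.** Add to SAP 9.3.5:

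> If item 5 is *None of the time* and item 6 is blank, item 6 is scored 0, stays in the denominator and does not count toward the limit of 2 missing symptom items. Recorded item 6 answers are kept as reported. Item 6 is treated as missed only if item 5 reports at least one attack or is itself missing.

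Optionally, apply the same to a blank item 8 when item 4 is *Not at all*, without overriding a recorded item 8 answer. This is minor. Keep the denominator deduction for items that were truly missed.

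SAP 2.7 says part of the study team has been unblinded. Document the change in the CSR, as SAP 9.1 already requires for changes after unblinding, and show the key secondary result under the present rule alongside.

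The cost is a few lines of text, one derivation step on item data already collected, and one extra table. Attack-free subjects will score slightly lower than under the present rule.
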